# 1 FLOW CHARTS

## 1.1 GRAPHICAL STUDY DESIGN

Abbreviations: HbA1c = hemoglobin A1c; N = number; R = randomization; T2D = Type 2 Diabetes; V = visit; W = week.

## 1.2 STUDY FLOW CHART

	Screening Period		Double-blind Treatment Period a											Follow-up Period b
	Screening	Run-in	Randomized Double-blind Core Treatment Period						Randomized Double-blind Extension Period					
VISIT	1	2	3	4	5	6	7	8	9	10	11	12	13	14
Week	-4	-2	0	3	6	12	18	26	39	52	68	86	104	106
Day (window [days])	-28	-14 (±3)	1	21 (±3)	42 (±3)	84 (±3)	126 (±3)	182 (±3)	273 (±7)	364 (±7)	476 (±7)	602 (±7)	728 (±3)	742 (±3)
Informed consent	X													
Inclusion criteria	X													
Exclusion criteria	X	X	X											
Patient demography	X													
Medical/surgical history	X													
Prior medication history	X													
Body weight, height c	X	X	X	X	X	X	X	X	X	X	X	X	X	X
Vital signs d	X	X	X	X	X	X	X	X	X	X	X	X	X	X
Physical examination:														
Complete	X							X					X	
Abbreviated e		X	X	X	X	X	X		X	X	X	X		X
Concomitant medication	X	X	X	X	X	X	X	X	X	X	X	X	X	X
SMBG f			X	X	X	X	X	X	X	X	X	X	X	X
Diet & exercise instruction		X	X					X		X	X	X		
Instruction on basic GU hygiene & hydration		X	X	X	X	X	X	X	X	X	X	X		
IRT contact	X	X	X	X	X	X	X	X	X	X	X	X	X	X
Randomization			X											

	Screening Period		Double-blind Treatment Period a											Follow-up Period b
	Screening	Run-in	Randomized Double-blind Core Treatment Period						Randomized Double-blind Extension Period					
VISIT	1	2	3	4	5	6	7	8	9	10	11	12	13	14
Week	-4	-2	0	3	6	12	18	26	39	52	68	86	104	106
Day (window [days])	-28	-14 (±3)	1	21 (±3)	42 (±3)	84 (±3)	126 (±3)	182 (±3)	273 (±7)	364 (±7)	476 (±7)	602 (±7)	728 (±3)	742 (±3)
Dispense glucose meter		X												
Dispense diary		X	X	X	X	X	X	X	X	X	X	X	X	
Collect/review diary			X	X	X	X	X	X	X	X	X	X	X	X
Dispense single-blind placebo		X												
Dispense double-blind IMP			X	X	X	X	X	X	X	X	X	X		
IMP accounting & compliance			X	X	X	X	X	X	X	X	X	X	X	
12-lead ECG g		X						X					X	
Laboratory assessmentsh														
Serum 25 hydroxyvitamin D screening	X													
FPG i			X	X	X	X		X		X		X	X	
HbA1c	X		X			X		X		X		X	X	
Safety laboratory	X		X	X	X	X		X		X		X	X	X
Hematology	X		X			X		X		X		X	X	X
Fasting lipids			X					X					X	
FSH and estradiol for documentation of menopausal status j	X													
Estradiol (only for women)			X					X		X			X	
Bone turnover markers k			X					X		X			X	

	Screening Period		Double-blind Treatment Period a											Follow-up Period b
	Screening	Run-in	Randomized Double-blind Core Treatment Period						Randomized Double-blind Extension Period					
VISIT	1	2	3	4	5	6	7	8	9	10	11	12	13	14
Week	-4	-2	0	3	6	12	18	26	39	52	68	86	104	106
Day (window [days])	-28	-14 (±3)	1	21 (±3)	42 (±3)	84 (±3)	126 (±3)	182 (±3)	273 (±7)	364 (±7)	476 (±7)	602 (±7)	728 (±3)	742 (±3)
Markers of calcium metabolism l			X					X		X			X	
Collection of home 24-hour urine for albumin, creatinine, albumin-creatinine ratio, calcium, magnesium, and phosphorus m			X					X		X			X	
Urinalysis w/microscopy n	X		X			X		X		X		X	X	
DXA scan o		X						X		X			X	
Evaluate for glycemic rescue	To be assessed and reported throughout the Treatment Period													
Hypoglycemia	To be assessed and reported throughout the study													
AE/SAE/AESI/EOSI recording p	To be assessed and reported throughout the study													

Abbreviations: AE = adverse event, AESI = adverse event of special interest, BMD = bone mineral density, BP = blood pressure, DXA = dual-energy X-ray absorptiometry, ECG = electrocardiogram, EOSI = event of special interest, EOT = End of Treatment, FPG = fasting plasma glucose, FSH = follicle-stimulating hormone, GU = genito-urinary, HbA1c = hemoglobin A1C, HR = heart rate, IMP = investigational medicinal product, iPTH = parathyroid hormone, IRT = Interactive Response Technology, NIMP = noninvestigational medicinal product, NTX = N-terminal telopeptide of Type 1 collagen, P1NP = Type 1 procollagen N-terminal propeptide, SAE = serious adverse event, SMBG = self-monitoring of blood glucose,  $\beta$ -CTX-1 = beta C-terminal telopeptide of Type 1 collagen.

- a If a patient discontinues treatment with IMP early during the Treatment Period, the patient will have a Premature EOT Visit, and a Follow-up Visit, 2 weeks after the last dose of IMP. However, every effort will be made to have the patients return to the site for all scheduled visits, in particular, the visits at Week 26 (Visit 8) and Week 104 (Visit 13). If the patient does not agree to a site visit, they will be contacted by telephone to inquire about safety status.
- b The Follow-up Visit will take place 2 weeks  $\pm$  3 days after the last dose of IMP. All attempts will be made to contact the patient to inquire about safety status.
- c Height to be measured only at Screening, Week 52, Week 104, and at the Premature EOT Visit.
- d Vital sign measurements (sitting BP and HR): 3 separate seated BP and HR measurements should be taken with at least 1 minute between readings, following a 5-minute rest period and prior to phlebotomy (see Appendix C).
- e The abbreviated physical exam should focus on cardiac and respiratory systems, as well as any areas important for assessment of AEs if necessary.

- f* Patients will be instructed to measure their fasting glucose levels via SMBG and discuss results with site personnel at clinic visits or phone contacts. The frequency of the fasting SMBG measurements will be determined by the Investigator according to the clinical need and background diabetes treatment, but it is recommended to be done at least once a week. Patients will also be instructed to self-assess blood glucose levels whenever they experience any illnesses (eg, cold, flu), or symptoms of hyperglycemia or hypoglycemia. Note that the SMBG measurements obtained with glucose meters are displayed as plasma glucose concentration. The SMBGs  $\leq 70$  mg/dL will be reported on the hypoglycemia specific electronic case report form page.
- g* The 12-lead ECG recordings should be obtained prior to IMP administration. The ECG will be evaluated as "normal" or "abnormal".
- h* All laboratory assessments occur prior to dose of double-blind IMP and NIMP.
- i* The FPG is performed in fasting status, ie, without any food intake (except for water) for at least 8 hours.
- j* The FSH and serum estradiol is performed in all women at Screening to confirm menopausal status as needed.
- k* Markers of bone turnover include: markers of bone resorption (serum NTX, serum  $\beta$ -CTX-1) and bone formation (serum P1NP and osteocalcin).
- l* Markers of calcium metabolism include: serum and urinary calcium (adjusted for creatinine), serum 25-hydroxyvitamin D, serum 1,25-dihydroxyvitamin D, serum and urinary phosphorus (adjusted for serum phosphorus, and creatinine), serum and urinary magnesium (adjusted for serum magnesium and creatinine), serum iPTH.
- m* 24-hour urine samples for calcium, phosphorus, and magnesium will be collected at Weeks 0, 26, 52, and 104. Patients will be instructed to initiate the 24-hour urine collection on the day before the visits. In exceptional situations, the 24-hour urine collection can be done up to 2 days maximum prior to or after the visit, and the specimen should be sent to the study site as soon as possible.
- n* Urinalysis will be done at central laboratory and includes urine dipstick and microscopy. Dipstick includes assessment of specific gravity, pH, protein, blood, ketones, bilirubin, urobilinogen, nitrite, and leukocyte esterase. Microscopy includes detection of formed cellular elements, casts, bacteria, yeast, parasites, and crystals in centrifuged urine sediment. In the event of abnormal urinalysis findings, urine cultures should be performed (microbial testing). Additionally, urine cultures should be performed if at any point the Principal Investigator suspects the presence of a urinary tract infection.
- o* Baseline DXA scans for BMD assessment will be performed during Run-in and centrally reviewed for eligibility assessment. All BMD assessments will be performed locally with a central review. Post-Baseline DXA scans will be performed within 2 weeks prior to the on-site visits at Weeks 26, 52, and 104, or no later than 7 days after the visit. Body composition by DXA will be performed at the same visits when the BMD is measured.
- p* All SAEs, AEs, AESI, and EOSI will be collected starting from signing informed consent and continue until the end of the study. All AEs that occur during treatment should be followed until study completion (or until patients leave the study) or until the event has resolved, the condition has stabilized or the patient is lost to follow-up. All patients will have a Follow-up Visit 2 weeks after the last dose of IMP to collect safety information.

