#### **9.1.4.5 Kidney function and calcium metabolism parameters**

Serum creatinine, 24-hour home-collected urine albumin, calcium (adjusted for creatinine), creatinine, phosphorus (adjusted for serum phosphorus and creatinine), magnesium (adjusted for serum magnesium and creatinine) will be assessed at Baseline (Visit 3), Week 26 (Visit 8), Week 52 (Visit 10), and Week 104 (Visit 13) (see [Section 1.2](#)). Serum creatinine will also be measured at Screening (Visit 1). Patients will be instructed to initiate the 24-hour urine collection on the day before the planned visits. In exceptional situations, the 24-hour urine collection can be done up to 2 days maximum prior or after the visit, and the specimen should be sent to the study site as soon as possible. Patients will be instructed to keep the 24-hour urine specimens at home in a cool place at room temperature, or refrigerated at 2°C to 4°C before they are sent to the site. The patient will be advised to refrain from heavy exercise or sex during the day of the collection. Specific details about specimen collection, storage, packaging, and shipping will be provided in the laboratory operational manual. A central laboratory will analyze samples and calculate the eGFR and UACR to allow assessment of change from baseline in eGFR and UACR. Details of urine collection and analysis are provided in [Section 9.1.4.5](#).

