## 10 STUDY PROCEDURES

### 10.1 VISIT SCHEDULE

The visit schedule and procedures/assessments are listed in the Study Flow Chart ([Section 1.2](#)). The aim of this section is to provide details on how some of the procedures/assessments should be performed.

This is an out-patient study and consists of 14 on-site visits. Additional on-site visits or telephone contacts can be scheduled at any time during the study whenever considered necessary by the Investigator.

The patients need to arrive at the study site in a fasting state for Visit 1, Visit 3, Visit 4, Visit 5, Visit 6, Visit 8, Visit 10, Visit 12, Visit 13, and Visit 14 unless instructed otherwise by the investigator. Throughout the study, “fasting” is defined as at least 8 hours without food (no food or liquid intake, other than water). **Note:** If the patient is not fasting at the visits specified above, the blood sample will not be collected and a new appointment should be given to the patient for the following day if possible, with instruction to be fasted. Other procedures can be performed as scheduled. All laboratory assessments will occur prior to IMP and NIMP administration on the day of the visit.

The Run-in Visit (Visit 2) can be performed up to 2 weeks ( $\pm 3$ ) days after the Screening Visit and once the results of all Screening tests are available and the patient is confirmed to be eligible for participation in the study. The visit windows for the Double-blind Treatment Period visits will be as follows: Visit 3 through Visit 8 should occur at the schedule  $\pm 3$  days; Visit 9 through Visit 12 should occur at the schedule  $\pm 7$  days. Visit 13 should occur at the schedule  $\pm 3$  days and Follow-up Visit (Visit 14) should occur within 2 weeks after last dose of IMP  $\pm 3$  days.

If one visit date is changed, the next visit should occur according to the original schedule, ie, calculated from the date of Baseline visit (Visit 3, Week 0).

For a complete list of procedures scheduled for each study visit please refer to the Study Flow Chart ([Section 1.2](#)), which details the procedures to be performed.

All data obtained during the study visits are reviewed by the Investigator and Sub-investigators who are qualified in treatment of T2D and are trained on the study.

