##### **10.1.1.2.1 Run-in Visit, Visit 2 (Week -2)**

The following procedures/assessments will be performed at Visit 2 (Week -2):

- Exclusion criteria are to be reviewed.
- Changes in concomitant medication are reviewed.
- Measurement of BW.
- Abbreviated physical examination.
  - The abbreviated physical examination should focus on cardiac and respiratory systems, (as well as any areas important for assessment of AEs, if necessary), and vital signs (SBP and DBP, and HR) (see [Appendix C](#) for details).
  - Diet and exercise instruction will be provided.
- Blood glucose meter is dispensed and instructions/training are provided.
- Patient diary is dispensed and instructions/training are provided.
- Instruction on glucose testing, basic genito-urinary (GU) hygiene and hydration, and recognizing DKA symptoms (see [Appendix B](#)) is provided.
- The IRT is notified for registration of Run-in Visit and allocation of single-blind Run-in kit.
- Run-in kit/placebo is dispensed.
- 12-lead ECG is conducted.
- AEs/SAEs/AESI/EOSI and hypoglycemia (if any) are reported.
- Patients are instructed to return to the site in the fasting state with used, partially used, or not used single-blind Run-in kit for Visit 3 (Randomization).

- Patients will be referred to DXA scan facility to perform DXA scan prior to Visit 3 (Randomization).
- Patients are provided with a urine container and instructed on how to collect 24-hour urine at home to be brought to the site at Visit 3 (Randomization).

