## 11.4 STATISTICAL METHODS

Continuous data will be summarized by treatment group using the number of observations available (N), mean, SD, minimum, median, and maximum.

Categorical data will be summarized by treatment group using count and percentage.

In general, descriptive statistics of quantitative efficacy and safety parameters (result and change from Baseline) by scheduled visits will be provided on observed cases (OC), ie, inclusion of only patients having nonmissing assessments at a specific visit.

The Baseline value is defined generally as the last available value before the first dose of double-blind IMP or the last available value prior to randomization for patients who were randomized but never exposed to IMP.

For serum creatinine and eGFR, the Baseline value is defined as average of all values before the first dose of double-blind IMP for those randomized and exposed or before randomization for patients who were randomized but never exposed to IMP.

Analysis of demographics and Baseline characteristics and prior and concomitant medications will be provided in detail in the Statistical Analysis Plan (SAP).

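### The after-visit allowance for the 24-hour urine also covers Week 0 and Week 104, so a late Week 0 collection conflicts with the pre-dose rules and can cost a patient every urinary change from Baseline

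*Protocol*

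**What the plan says.** Protocol Section 1.2, footnote m, names the timepoints: "24-hour urine samples for calcium, phosphorus, and magnesium will be collected at Weeks 0, 26, 52, and 104". The normal instruction is that "Patients will be instructed to initiate the 24-hour urine collection on the day before the visits". The exception follows: "In exceptional situations, the 24-hour urine collection can be done up to 2 days maximum prior to or after the visit". Section 9.1.4.5 names Baseline (Visit 3) and Week 104 (Visit 13) among the collection visits, covers albumin and creatinine as well as the minerals, and repeats the exception: "In exceptional situations, the 24-hour urine collection can be done up to 2 days maximum prior or after the visit". SAP Appendix D, footnote m, carries the same rule. None of these places treats Week 0 or Week 104 differently from Weeks 26 and 52.

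Other text points the opposite way at Week 0:

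- Footnote h of the same flow chart: "All laboratory assessments occur prior to dose of double-blind IMP and NIMP".
- Protocol 10.1: "All laboratory assessments will occur prior to IMP and NIMP administration on the day of the visit".
- Protocol 8.4 has baseline assessments finished before the randomization call is made.
- Protocol 10.1.1.2.1 has the patient bring the completed home collection to Visit 3.
- Protocol 11.4: "The Baseline value is defined generally as the last available value before the first dose of double-blind IMP". Protocol 9.2 and SAP 2.5.4 give the same definition.

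**The concern.** At Weeks 26 and 52 a patient still on treatment is taking drug on both sides of the visit, so a day or two either way does little harm. The other two timepoints differ. Visit 3 is where double-blind drug is handed out, and Visit 13 is where it ends. A window that is symmetric around those visits crosses the start or the end of treatment.

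At stake are the changes from Baseline in UACR, which is an other efficacy endpoint, and in urinary calcium, phosphorus and magnesium, which are safety endpoints. Protocol 9.4 justifies looking at calcium metabolism by the drug's action on the renal tubule, so the urinary minerals bear on how any change in bone density would be read.

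**Working it through.** The documents state no sample size or precision for the urinary endpoints, so there is no figure of the plan's to reproduce. The check is mainly a comparison of texts, visit by visit.

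**Week 0.** Take the first dose on the day of Visit 3, which is Day 1 under SAP 2.5.4. A collection made 1 to 2 days after the visit then falls on Days 2 to 3, wholly after the first dose.

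1. Footnote m and Section 9.1.4.5 allow it. Footnote h and Sections 8.4 and 10.1 do not.
2. Under the baseline definition the result cannot serve as Baseline.
3. The flow chart shows no 24-hour urine before Visit 3, so there is no earlier value to use.
4. SAP 2.5.3 makes a change from Baseline missing when the baseline value is missing. The baseline imputation in SAP 2.4.4.2 is for the continuous secondary efficacy endpoints, and that in 2.4.5.1 is for BMD. UACR is summarized on observed values (SAP 2.4.4.3), and no imputation is planned for the urinary minerals.
5. The loss per affected patient is 4 measures x 3 visits (Weeks 26, 52, 104) = 12 change values.

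A collection that begins before the first dose and ends after it is not classified anywhere.

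**Size at Week 0.** The documents give no rate of late collection. Let f be the assumed share of patients late at Week 0. With 120 per arm, the number lost is 120 x f. The relative widening of a confidence interval is 1/√(1 − f) − 1.

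| f (assumed) | Lost per arm | Interval widening |
|---|---|---|
| 2% | 2.4 | 1.0% |
| 5% | 6 | 2.6% |
| 10% | 12 | 5.4% |

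**Weeks 26 and 52.** For patients still on treatment, drug continues on both sides of the visit, so there is no problem.

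**Week 104.** The flow chart dispenses no drug at Visit 13, and Protocol 8.9 provides none after end of treatment. A post-visit collection in a completer therefore follows the last dose. It is still used as the Week 104 value:

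- SAP 2.1.3 keeps efficacy data regardless of drug discontinuation.
- The Week 104 analysis window in SAP 2.5.4 is Day 665 onward.
- By-visit laboratory summaries use the treatment-emergent period, which runs 10 days past the last dose (SAP 2.1.4 and 2.5.4).

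For the degree of washout, Protocol 9.2 equates 10 days with about 5 half-lives in moderate renal dysfunction, so the half-life is about 10/5 = 2 days there. The remaining drug is 0.5^(days/half-life).

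| Days after last dose | Half-life 2 days | Half-life 1 day (assumed) |
|---|---|---|
| 1 | 71% | 50% |
| 2 | 50% | 25% |
| 3 | 35% | 12.5% |

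This is partial washout of drug. The documents do not say how quickly the effect on urinary excretion follows.

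**Comparison within the protocol.** Footnote o on DXA limits its after-visit allowance to post-Baseline scans and places the baseline scan in Run-in. Footnote m has no such limit.

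**The case against.** The allowance is for exceptional situations, and the default is collection begun the day before, with the Week 0 container brought to Visit 3. A site collecting after the first dose would breach footnote h and Sections 8.4 and 10.1. The protocol therefore gives two conflicting instructions and does not plainly license a post-dose baseline. That stands, and it makes this a contradiction to reconcile.

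A reader might infer that late specimens bias the active arms by building early drug effect into their baselines. The documents do not support this as the planned outcome. A wholly post-dose value is already excluded as Baseline, so what follows is a missing change. Contamination would need specimens to be labelled by visit and not by collection time, or a straddling collection to be accepted.

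A reader might also add late shares at the two visits, say 5% at Week 0 and 5% at Week 104, and conclude that the treatment difference shrinks by 10%. That fails on two counts. Patients whose baseline is rejected leave the change analysis and do not dilute it. The sum also assumes that the effect is gone within 2 days, whereas the only half-life the documents imply leaves about half the drug at that point.

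Keeping off-drug data is deliberate for patients who discontinue. In a completer, an off-drug Week 104 urine is only a product of the visit window.

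Finally, Section 9.1.4.5 refers to a laboratory manual that is not among these documents. It may already restrict Week 0.

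**Conclusion.** The point holds as a limited defect of timing and data handling. At Week 0 the after-visit allowance contradicts the pre-dose rules and the baseline definition. Its normal consequence is the loss of all 12 urinary change values for the patient concerned, and the straddling collection is left undefined. At Week 104 some completers' values may reflect partial washout.

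The size cannot be fixed from the documents. The 2% to 10% range is an assumption, the Week 0 arithmetic takes the first dose on the day of Visit 3, and no attenuation figure is supported. UACR and the urinary minerals are descriptive only (Protocol 11.4.2.3 and 11.4.3) and lie outside the testing hierarchy. Serum calcium-metabolism markers and bone turnover markers are blood tests and are not affected. The change is still worth making because it is nearly free and a lost baseline cannot be recovered.

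**What to change.** In Protocol footnote m, Section 9.1.4.5 and SAP Appendix D:

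- Limit the after-visit allowance to post-Baseline collections, as footnote o does for DXA.
- Require the Week 0 collection to be completed before the first double-blind dose, with up to 2 days before Visit 3 allowed.
- For patients still on IMP at Visit 13, allow only the before-visit side.
- Record the start and stop date and time of each collection.
- In the SAP, set baseline and on-treatment status from those times, and state that a collection ending after the first dose is not a baseline.

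Impose no on-drug collection rule at the Premature EOT Visit, which under Protocol 10.3.3 and 10.3.4 may follow discontinuation. Impose none on patients who have already stopped but are still asked to attend Week 104 (Protocol 6.2.2). Such a rule could not be met and would discard data the plan wants.

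The cost is a few sentences and the time fields, if they are not already captured. Containers are already issued at Visits 2 and 12, so the before-visit side is workable. The downside is an occasional repeat container or a short delay before the first dose. The Run-in extension in Protocol 10.1.1.2 is meant for eligibility assessments and should not be counted on to absorb that delay.
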